1. PROTOCOL SUMMARY

1.1. Synopsis

Title: Evaluation of a Wetness Sensing System for Continence Care

Study Description: The investigational product to be evaluated in this study is FitRight® Connect™ Wetness Sensing System which includes: the FitRight® Connect™ Pod, the FitRight® Connect™ App, the FitRight® Connect™ charger/adapter and the FitRight® Connect™ Sensing Brief- (Medline Industries, LP) henceforth, referred to as FitRight® System, Pod, App, Charger, Alert Indicator and Brief. The purpose of this study is to validate the FitRight System sensor's ability to detect when an adult brief has absorbed enough liquid (~90-360 milliliters (mL)) normal saline via simulated urinary void to trigger an alert to change the brief.

Phase: This is a prospective single center post-marketing study investigating the performance and user acceptance of the FitRight® System.

Objectives: Primary Objective: To evaluate the FitRight® System sensor's ability to detect when an adult brief has absorbed enough liquid (~90-360 mL) normal saline via a simulated urinary void to trigger an alert to change the brief in the sitting, supine, and right or left side positions.

Secondary Objective: To determine the FitRight® Brief's residual volume capacity. In a subset of 22 participants, evaluate the FitRight® Brief after the brief has absorbed the maximum amount of liquid normal saline via a simulated urinary void (360 mL) in the sitting position and then weighed via the rewet procedure.

Endpoints: Primary Endpoint: The number of FitRight® System alerts when 90-360 mL normal saline has been absorbed into the brief in the sitting, supine, and right or left side positions.

Secondary Endpoint: The weight of the filter paper after performing the rewet test with the FitRight® Brief after absorbing 360 mL of normal saline via a simulated void.

Study Population: Fifty-six healthy, normal, adult volunteers

Inclusion criteria: Healthy individuals who meet all of the following criteria will participate in this study:

- Individuals ≥ 18 years of age
- Individual can dress and undress self with no assistance
- Individuals can ambulate without assistance
- Individual can sit unsupported in a chair or on bedside with no assistance
- Individual can lay supine and propel self up with no assistance
- Individual can lie left/right lateral and propel self up with no assistance
- Individuals who have hip dimensions between 32" and 70" (81– 178 cm)

Exclusion criteria: Individuals who meet any of the following criteria will not be allowed to participate in this study:

- Individual is sensitive to the components of the study product(s).
- Individual is considered inappropriate by the Principal Investigator (PI).
- Individual has self-reported current skin condition(s) or issues around the sacral or perineal areas, such as open sores, sacral pressure injuries, rash, burns, surgical wounds and/or compromise of skin integrity.
- Individuals who cannot complete all phases of the study requirements.
- Individual requires use of an absorbent undergarment or catheter as the primary incontinence management strategy
- Individuals who are pregnant

Description of Sites/Facilities Enrolling

Rochester Clinical Research located in Rochester, NY

Participants:

Fifty-Six Participants

Description of Study design:

Each participant will be provided with the FitRight® System for the duration of the study. The study products will be used to collect real-life measurement data in order to assess the FitRight® System. Each participant will be asked to wear at least three briefs so that they are wearing each brief during the simulated voids performed by the site staff.

The site staff will perform the simulated void by addition of (90-360 mL normal saline to the brief. The FitRight® System will be assessed for alerts while participants are in the

following positions: supine, sitting, and laying on either left or right side. Each participant will be randomized to either the left or right side. Twenty-two of the fifty-six participants will perform rewet testing procedures. The study results will be used to assess the reliability of the device's absorption to trigger an alert.

Participant Duration: Approximate time will be two hours for each participant to complete the procedures.

1.2 Schedule of Activities (SOA)

Study Timeline of Events ^a	Pre-Study	During the Study	End of the Study
Informed Consent	X		
Verification of eligibility	X		
Randomization	X		
Participant applies first brief with tubing (study staff checks for correct application) and participant sits in sitting position.		X	
Study staff pours 90mL saline and starts timer for five minutes.		X	
After five minutes, staff records whether an alert was triggered. Staff pours an additional 150mL saline and starts a timer for five minutes. ^{b, c}		X	
After five minutes, staff records whether an alert was triggered. Staff pours an additional 120mL saline and starts a timer for five minutes. ^{b, c}		X	
After five minutes, staff records whether an alert was triggered. Staff pours an additional 120mL saline and starts a timer for five minutes. ^{b, c}		X	
After five minutes, staff records whether an alert was triggered. ^d		X	

Participant removes the first brief and applies second brief with new tubing (study staff checks for correct application) and participant lays in supine position.		X	
Study staff pours 90mL saline and starts timer for five minutes.		X	
After five minutes, staff records whether an alert was triggered. Staff pours an additional 150mL saline and starts a timer for five minutes. ^{b, c}		X	
After five minutes, staff records whether an alert was triggered. Staff pours an additional 120mL saline and starts a timer for five minutes. ^{b, c}		X	
After five minutes, staff records whether an alert was triggered. Staff pours an additional 120mL saline and starts a timer for five minutes. ^{b, c}		X	
After five minutes, staff records whether an alert was triggered. ^d		X	
Participant removes the second brief and applies third brief with new tubing (study staff checks for correct application) and participant lays in their randomized side position (either left or right side).		X	
Study staff pours 90mL saline and starts timer for five minutes.		X	
After five minutes, staff records whether an alert was triggered. Staff pours an additional 150mL saline and starts a timer for five minutes. ^{b, c}		X	
After five minutes, staff records whether an alert was triggered. Staff pours an additional 120mL saline and starts a timer for five minutes. ^{b, c}		X	
After five minutes, staff records whether an alert was triggered. Staff pours an additional 120mL saline and starts a timer for five minutes. ^{b, c}		X	
After five minutes, staff records whether an alert was triggered. Participant will remove brief ^d		X	
All participants will complete steps above. Only the first 22 participant will go on to complete the following steps.			

Participant applies new brief (study staff checks for correct application) and participant is in sitting position. ^a		X	
Study staff pours 360 mL saline into the brief and starts a timer for ten minutes. ^b		X	
After ten minutes, participant removes brief and gives it to the staff. ^c		X	
Staff weighs out at least 10.0 grams filter paper and records the weight. Staff places the filter paper centered on the wet brief and over the acquisition and dryness layer (ADL) places the calibrated weight on the filter paper and starts a timer for one minute.		X	
After one-minute, calibrated weight and filter paper is removed and the filter paper is weighed, and the weight is recorded.		X	
Study staff will complete steps below for all participants.			
Evaluation for adverse events	X	X	X
Participant dismissal			X
^a Study activity will occur after informed consent has been signed and the participant has met all the inclusion criteria and none of the exclusion criteria.			
^b This pour will only occur if the previous pour(s) did not trigger an alert. If the previous pour did trigger an alert the participant will either move to the application of the next brief or the participant will be dismissed if they are at the end of their participation.			
^c If the Pod alerts prior to the fourth pour, it is considered a pass. If it doesn't alert after five minutes post the third pour, it is a failure. Note: There is no minimum pour volume for the first alert.			
^d Whether there was an alert triggered or not, participant will either move to the application of the next brief or the participant will be dismissed if they are at the end of their participation.			
^e This step is part of the rewet testing. Only the first 22 participants enrolled in the study will perform the rewet testing.			

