2.2 Study Product(s)

The investigational product being evaluated in this study is the FitRight® Connect™ Wetness Sensing System that includes the FitRight® Connect™ Pod, FitRight® Connect™ App, FitRight® Connect™ charger/adapter and FitRight® Connect™ Brief.

2.2.1. Product Overview:

The FitRight® Pod is a wearable sensor that monitors adult briefs for wetness and notifies caregivers when a resident becomes wet. In doing so, the FitRight® System may remove the need for caregivers to unnecessarily check residents while simultaneously ensuring residents are changed promptly as required. The FitRight® Pod is reusable and works by attaching to the outside of the FitRight® Brief. From the outside of the brief, the FitRight® Pod is able to monitor for and characterize moisture on the inside of the brief using a technique called impedance sensing.

The FitRight® Pod then transmits information wirelessly to a Wi-Fi enabled tablet. At a glance, caregivers can view the residents under their care, see who is wet and therefore requires immediate attention, and who is dry and shouldn't be disrupted.

2.2.2 Product Description:

The FitRight® System is used to help monitor and alert caregivers when it is appropriate to change the FitRight® Brief. The FitRight® System is composed of a wetness sensing brief, a pod that connects to Wi-Fi, and software that displays alerts on a display (FitRight® App). The FitRight® Brief is a wetness detection brief that is a non-sterile, disposable, single use device with a reusable wetness alert sensor (FitRight® Pod).

The FitRight® System alerts caregivers when a patient has micturated within the FitRight® Brief. An ink-based sensor is printed on the poly backsheet layer of the FitRight® Brief and when urine contacts the ink for a predetermined amount of time, it sends an alert to the FitRight® Pod that is attached on/secured to the outside of the FitRight® Brief. The FitRight® Pod translates that alert (via Wi-Fi) to the software application using a cloud-based server that is loaded on to a display device chosen by the user.

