4 STUDY DESIGN

4.1 Overall Design

The purpose of this study is to validate the FitRight® Sensor's ability to detect when an adult brief has absorbed enough liquid (90-360 mL normal saline via simulated urinary void) to trigger an alert to change the brief. Data will be collected from healthy, normal, adult volunteers and will be used to assess the device's absorption and ability to trigger an alert.

Each participant will be provided with the FitRight® System for the duration of the investigation. Briefs will be used to collect real-life measurement data in order to validate the FitRight® System algorithms and the FitRight® Alert Indicator.

Each participant will be measured for the appropriately sized briefs using the participant's hip dimension and will wear this size throughout the study. Three sized briefs will be worn in three different positions (sitting, laying supine, and laying on either left or right side) in order to determine the efficacy of the FitRight® Alert Indicator. Participants will apply the briefs themselves and study staff will confirm correct application. Tubing will be setup in order to apply normal saline directly to the center of the brief.

Study staff will pour 90mL normal saline (first pour) to the brief via the tubing and will start a timer for five minutes. After five minutes, study staff will record whether the FitRight® Alert Indicator triggered an alert. Note: there is no minimum volume for the alert. If the alert does trigger, participant will remove the brief and apply the next brief for the next position. If the alert did not trigger, study staff will apply 150mL normal saline (second pour) and will start a timer for five minutes. After five minutes, study staff will record whether the FitRight® Alert Indicator triggered an alert. If the alert does trigger, participant will remove the brief and apply the next brief for the next position. If the alert did not trigger, study staff will apply 120mL normal saline (third pour) and will start a timer for five minutes.

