After five minutes, study staff will record whether the FitRight® Alert Indicator triggered an alert. If the alert does trigger, participant will remove the brief and apply the next brief for the next position. If the alert did not trigger, study staff will apply 120mL normal saline (fourth pour) and will start a timer for five minutes. After five minutes, study staff will record whether the FitRight® Alert Indicator triggered an alert. Whether the FitRight® Alert Indicator triggered an alert or not, the participant will remove the brief and apply the next brief for the next position. Study staff will record whether the brief passed or failed to indicate. If the brief triggered an alert within the five minutes after the first, second, or third saline pour and prior to the fourth pour, the brief passed. If the brief did not trigger an alert by five minutes after the third pour, the brief fails. The fourth pour, if required, will help to determine if more volume was needed to trigger the alert or if the brief was defective.

The first 22 participants enrolled in the study will perform the rewet procedures. Participants will apply the sized brief and study staff will confirm correct application. Tubing will be setup in order to apply normal saline directly to the center of the brief. Study staff will pour 360 mL normal saline to the brief via the tubing and will start a timer for ten minutes. After ten minutes, participants will remove the brief and give the brief to the study staff. Study staff will weigh out at least 10.0 grams(g) filter paper (and as close to 10.0g as possible) and record the weight. Study staff will apply the filter paper centered on the wet brief and over the ADL layer, , apply a calibrated weight to the top of the filter paper, and start a timer for one minute. After one minute, the study staff will remove the calibrated weight and filter paper and weigh the wetted filter paper and record the weight. If any leakage or fluid infusion related issues occur during rewet testing this will be considered an invalid test (test failure) and this case will not be counted toward the 22 cases needed for rewet testing The data will still be recorded.

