6.4.1. Application of the FitRight Wetness Sensing System

Participants will be measured for their hip circumference. Participants will be given the brief for their size (available sizes are medium-2XL) that corresponds to the circumference measurement. Study staff will use their discretion to select the applicable size. Study staff will record on the CRF which size was provided to the participant. Following the IFU, participants will be given space to privately apply the FitRight® Brief and tubing. Once the brief is on and tubing is in place, study staff will apply exam gloves and assess the brief for correct application. If the brief or tubing needs to be adjusted, participants will be given more time to privately make adjustments. The tubing should be placed directly in the center of the bottom of the brief at the approximate location of urination.

Once the tubing is in place and the brief is applied correctly, participants will be instructed to sit on the bed in a sitting position. If the tubing moves, participants should again adjust the tubing to the correct position. Study staff will then apply the FitRight® Pod to the brief according to the IFU and make sure that the FitRight® App is indicating the Pod is connected. Once the FitRight® Pod and FitRight® App are properly setup, study staff will connect the tubing in the brief to the tubing connected to the funnel system.

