6.4.2 Normal Saline Pours

Once the FitRight® System and tubing is properly setup on the participant, the study staff will pour 90 milliliters (mL) of normal saline (first pour) through the funnel system to enter the brief. Study staff will immediately start a calibrated timer for five minutes once the saline drains from the funnel system. After the five minutes, study staff will document whether the brief did or did not trigger an alert. If the brief triggers an alert, the brief passes and the participant is ready for the next brief. If the brief does not trigger an alert, study staff will pour an additional 150mL normal saline (second pour) through the funnel system and will immediately start a calibrated timer for five minutes once the saline drains from the funnel system.

After the five minutes, study staff will document whether the brief did or did not trigger an alert. If the brief triggers an alert, the brief passes and the participant is ready for the next brief. If the brief does not trigger an alert, study staff will pour an additional 120mL normal saline (third pour) through the filtration system and will immediately start a calibrated timer for five minutes once the saline drains from the funnel system.

After the five minutes, study staff will document whether the brief did or did not trigger an alert. If the brief triggers an alert, the brief passes and the participant is ready for the next brief. If the brief does not trigger an alert, the brief fails, and study staff will pour an additional 120mL normal saline (fourth pour) through the funnel system and will immediately start a calibrated timer for five minutes once the saline drains from the funnel system. After the five minutes, study staff will document whether the brief did or did not trigger an alert. No matter if the brief did or did not trigger an alert, the participant will move onto the next brief. The fourth pour, if required, will help to determine if more volume was needed to trigger the alert or if the system was defective.

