8.7 Derived Variables

A variable will be created to indicate if a test should have passed for a given volume of fluid added to the brief. Correct pass=1 if a minimum of 90mL of fluid, else correct pass=0.

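### Alert status on the dry brief is not recorded, so the Section 8.7 reference is constant and a new alert cannot be told from one already showing

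*Combined protocol and SAP*

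**What the plan says.** - **Set-up (Section 6.4.1).** Staff attach the Pod and "make sure that the FitRight® App is indicating the Pod is connected". Nothing asks them to note whether an alert is showing, or says what to do if one is.
- **First pour (Section 6.4.2).** "the study staff will pour 90 milliliters (mL) of normal saline (first pour) through the funnel system to enter the brief". The timer starts when the funnel has drained, and alert status is first documented five minutes later.
- **Pass rule in the Schedule of Activities, footnote c.** "If the Pod alerts prior to the fourth pour, it is considered a pass". The footnote ends: "Note: There is no minimum pour volume for the first alert".
- **Pass rule in Section 4.1.** The section has a similar note ("Note: there is no minimum volume for the alert"), but its pass definition is narrower and covers only one that "triggered an alert within the five minutes after the first, second, or third saline pour and prior to the fourth pour, the brief passed".
- **Reference variable (Section 8.7).** "Correct pass=1 if a minimum of 90mL of fluid, else correct pass=0". Section 8.9.1 sets the pass/fail results against this variable within the primary reliability analysis (Cronbach's alpha, which for pass/fail data is KR-20).
- **Recorded volumes (Sections 8.5.1 and 8.6).** 90, 150, 120 and 120 mL, with no 0 mL level. The fourth brief, used for rewet testing, is worn without a Pod (Section 6.4.3), so it gives no dry reading either.

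**The concern.** The plan defines a class of tests that should not alert and then collects no observation in it. Two things follow.

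First, the primary comparison has nothing to compare with, because its reference never varies. Second, an alert seen after fluid shows detection only if the alert was off beforehand, and that is not recorded. The product claim also has a dry side: "At a glance, caregivers can view the residents under their care, see who is wet and therefore requires immediate attention, and who is dry". Section 2.1 gives needless night-time checks of dry residents as part of the rationale. As planned, the study yields a detection percentage but no estimate of false alerts, and it cannot show that the percentage is free of them.

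**Working it through.** **Inputs.** 56 participants (Section 8.1), three Pod-monitored briefs each (Section 4.1), up to four pours per brief (Section 6.4.2). Brief tests: 56 × 3 = 168. Readings: at most 168 × 4 = 672.

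**The plan's own figure.** Section 8.1 chooses N = 56 for a 95% interval on the pass proportion at 0.85, 0.90 and 0.95. The exact (Clopper-Pearson) widths at 56 are 0.202, 0.174 and 0.134. At 64, also a multiple of 8, they are 0.188, 0.162 and 0.124. With no stated width target or cap, 56 can be neither reproduced nor refuted. The present point does not depend on it.

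**Step 1: the Section 8.7 variable.** Per-pour volumes 90, 150, 120, 120 give 1, 1, 1, 1. Cumulative volumes 90, 240, 360, 480 also give 1, 1, 1, 1. The 'else' class occurs in 0 of 168 briefs and 0 of up to 672 readings.

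**Step 2: KR-20 against a constant.** KR-20 = k/(k−1) × [1 − Σpq / var(total)]. Take k = 2 items, the observed result (pass rate p) and the reference (always 1).
- Σpq = p(1−p) + 1×0 = p(1−p).
- Adding a constant leaves the variance unchanged, so var(total) = p(1−p).
- KR-20 = 2 × [1 − 1] = 0 whenever results vary, including at 85%, 90% and 95%. If every brief passes it is 0/0, undefined.

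**Step 3: the two pass rules.** Footnote c has an upper bound (the fourth pour) and no lower one. Section 4.1 has a lower bound (after a pour). For an alert already on before the first pour, footnote c gives a pass; Section 4.1, read strictly, does not. The only recorded item is status at five minutes, so if the alert stays on until then the data cannot apply the stricter rule.

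**Step 4: size of the possible inflation.** Let f be the proportion of briefs alerting when dry and still alerting at five minutes, and s the detection rate in the rest. Observed pass rate = f + (1−f)s. The documents give neither f nor s, so these are assumed ranges:

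| s | f = 0 | f = 0.1 | f = 0.2 | f = 0.5 | f = 1 |
|---|---|---|---|---|---|
| 0.70 | 0.700 | 0.730 | 0.760 | 0.850 | 1.000 |
| 0.80 | 0.800 | 0.820 | 0.840 | 0.900 | 1.000 |
| 0.90 | 0.900 | 0.910 | 0.920 | 0.950 | 1.000 |

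At f = 1 the result is 168/168 (exact 95% CI 97.8 to 100%). A less extreme case is one faulty Pod. Section 6.4.5 allows 12 disinfections per Pod, one between participants. If such a Pod served 12 participants, it would supply 12 × 3 = 36 of 168 passes (21%). With s = 0.80 elsewhere, the pass rate would be (36 + 132 × 0.80)/168 = 84.3%.

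**Step 5: what a dry reading would give.** With no alerts in n readings, the exact two-sided 95% upper limit is 1 − 0.025^(1/n): 2.2% for n = 168 treated as independent, 6.4% for n = 56. The chance of seeing at least one false alert is 1 − (1−f)^n. At a true rate of 1% this is 81.5% (168) or 43.0% (56); at 5% it is over 99.9% or 94.3%.

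**The case against.** - **Section 4.1 already excludes a pre-pour alert.** On its wording, yes. Footnote c is also attached to rows that follow a pour, and its remark on minimum pour volume need not mean 0 mL. So one cannot say that the plan as a whole accepts dry alerts. What stands is that the two rules differ and that the recorded data cannot enforce the narrower one.
- **Staff do look at the App before pouring.** They do, so it would be wrong to say that no reading takes place. An alert might be noticed, and the CRF and instructions for use are separate documents not available here. Still, the plan gives no field or rule for recording it.
- **The objective is detection only.** Sections 1.1, 3 and 4.1 do limit it to 90–360 mL, which lowers the priority of a false-alert estimate. It does not rescue Sections 8.7 and 8.9.1, which rely on whether a test should have alerted.
- **All Pods would have to be faulty to reach 168/168.** True. At 12 participants per Pod, 56 participants need at least five Pods (56/12 = 4.7), so a single faulty Pod affects only part of the sample.

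**Conclusion.** The point holds in this form: dry alert status is not recorded, the Section 8.7 reference is constant, the Section 8.9.1 comparison with it is uninformative, and the two pass rules conflict. These follow from the documents without further assumption, except that the comparison is read as a two-item KR-20.

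A reader might infer more than the documents support:

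- **That the pass rate is biased upward.** This happens only if dry alerts occur and last until the five-minute record. The documents give no dry-alert rate and do not describe latching or reset. The table above shows what would follow, not what will.
- **That the planned comparison cannot be computed.** It can, and returns 0, unless every brief passes. The pass percentages in Section 8.5.3 can be computed in any case.
- **That an always-alerting Pod gives a perfect result on every measure.** This is true of the alert count and pass percentage, not of KR-20, which would then be undefined.

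The change should be made: the affected analysis is primary and the remedy is small.

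**What to change.** 1. **Sections 6.4.1 and 6.4.2 and the CRF:** for each brief, record alert yes/no after the Pod shows as connected and immediately before the first pour. Add a 0 mL level in Sections 8.5.1 and 8.6.
2. **Footnote c and Section 4.1:** reconcile them so that a pass is an alert that first appears after pour 1, 2 or 3. A brief already alerting at 0 mL is a false alert: it stays in the denominator and is not a pass. Add a sensitivity analysis excluding such briefs.
3. **Sections 8.7 and 8.9:** include the 0 mL readings, which then fill the 'Correct pass' = 0 class. In place of KR-20 against a constant, report the 0 mL false-alert proportion and the pass proportion, each with a 95% CI that allows for three briefs per participant. If no false alert is seen, give the exact limits on both 168 and 56 readings. Neither limit covers clustering from reuse of the same Pods.

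**Cost.** One tick box per brief and a few lines of SAP text. The pass rate may fall slightly.

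**Limit of the fix.** Section 2.2.2 says the sensor alerts only after contact for a set time, so an immediate reading finds alerts already present and does not estimate the false-alert rate over wear. A five-minute dry interval per brief would strengthen it. Timers now total at most 3 × 4 × 5 + 10 + 1 = 71 minutes; adding 3 × 5 = 15 gives 86. Drainage, set-up and brief changes come on top, so a fit within the approximate two hours in Section 1.1 is not shown.
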